## 7.2.2. Immune Tolerance Induction Period

The first dose of rFVIIIFc ITI will be administered at the Baseline Visit, and treatment will continue until ITI success is declared or for a maximum of 48 weeks (12 months). The ITI regimen consists of rFVIIIFc 200 IU/kg/day ( $\pm$ 8 hours), which may be given as once-daily injections or divided into several injections per day at the discretion of the Investigator.

Subjects will visit the clinic 2 and 4 weeks after enrollment and then every fourth week until 48 weeks (12 months) or until a negative inhibitor ( $<0.6$  BU/mL) has been obtained. After the negative inhibitor results, visits will be scheduled every other week until ITI success or failure is declared.

The Investigator's assessment of ITI outcome will be based on results from the local laboratory. If the local laboratory results are inconclusive, the Investigator may use the central laboratory results to determine ITI outcome. During the ITI Period, subjects will undergo procedures and assessments at designated visits per [Table 1](#). Samples for inhibitor testing and assessment of FVIII activity levels will be analyzed at the local laboratory and at the central laboratory. Investigator treatment and assessment of inhibitor status will be based on results from the local laboratory. Negative inhibitor testing results must be confirmed (i.e., 2 consistent results at 2 consecutive assessments). See Section [7.2.2.2](#) for specific definitions of ITI outcomes.

The assessment of ITI outcome is illustrated in [Figure 2](#). After the subject has demonstrated a negative inhibitor ( $<0.6$  BU/mL) at 2 consecutive assessments within 2 weeks ( $\pm$ 3 days) per the schedule listed in [Table 1](#), an evaluation of rFVIIIFc IR will be performed at the next scheduled visit (the interpretation of the IR result will be performed after the negative inhibitor titer is confirmed, but the sample for IR is drawn at the visit for the confirmatory negative inhibitor titer). After  $IR \geq 1.32$  IU/dL per IU/kg ( $\geq 66\%$  of the expected IR) has been obtained at 2 consecutive assessments within 2 weeks ( $\pm$ 3 days), together with a sustained negative inhibitor titer ( $<0.6$  BU/mL), PK assessments to determine rFVIIIFc  $t_{1/2}$  will be performed at the subsequent visits until  $t_{1/2} \geq 7$  hours is attained. If  $t_{1/2} < 7$  hours is attained, subjects need to return to clinic within 2 weeks ( $\pm$ 3 days) to complete another  $t_{1/2}$  assessment until ITI success or 48 weeks (12 months).

Subjects are required to have at least a 24-hour washout prior to the IR and the PK assessment for  $t_{1/2}$ . The dose for IR and  $t_{1/2}$  is 50 IU/kg of rFVIIIFc based on actual potency. Investigators will advise subjects to delay any dose of rFVIIIFc until after scheduled inhibitor assessments. Investigators will also advise subjects to delay the remainder of their daily dose of rFVIIIFc until after IR and  $t_{1/2}$  assessments have been made.

Only subjects who achieve confirmed ITI success within 48 weeks (12 months) will continue into the Tapering and Follow-Up Periods. Throughout the study, FVIII activity levels above 200 IU/dL (based on local laboratory values) should be avoided. However, if FVIII activity levels rise above 200 IU/dL after the inhibitors are negative but before all of the ITI success criteria are met, the dose may be adjusted according to Investigator judgment to maintain the FVIII activity levels between 100 and 200 IU/dL. This dose reduction will not be considered part of the Tapering Period, and the subject will maintain the schedule of assessments per the ITI Period. See Section [11.1](#) for dosing details.

CONFIDENTIAL

The information contained herein may not be used, disclosed, or published without the written consent of Bioverativ Therapeutics Inc.

Page 39

Throughout the ITI Period, rFVIIIFc administration, bypassing agent administration, and any bleeding episodes will be collected by the subject and/or his caregiver in a study-specific electronic patient diary (EPD). EPD data will be reviewed by the Investigator on an ongoing basis and discussed with the subject at each visit.

#### **7.2.2.1. Use of Bypassing Agents**

In the time period between the subject's signing the ICF and the beginning of ITI treatment, treatment with bypassing agents (aPCC [FEIBA] or rFVIIa [NovoSeven]) is permitted.

During ITI treatment, subjects may also receive bypassing agents as needed for control of active bleeding at the discretion of the Investigator and within labeled dosing recommendations for the specific bypassing agent.

The Investigator may also prescribe bypassing agents if there is a high clinical suspicion of bleeding or potential for bleeding. When possible, bleeding should be confirmed via physical examination and/or imaging prior to administration of a bypassing agent; Confirmation of bleeding should not cause any unnecessary delay in the start of treatment, as judged by the Investigator.

In the event of an emergency, prior consultation with the Investigator is not required before administration of a bypassing agent; however, the Investigator must be notified of such use.

The use of bypassing agents in the setting of ITI requires awareness of FVIII activity levels and close monitoring for cessation of bleeding events.

In subjects with high-titer inhibitors, bleeding may be treated with bypassing agents, which can bypass FVIII inhibition. In subjects with low-titer inhibitors, bleeding events may be controlled with increased doses of replacement FVIII to overwhelm the inhibitor by antigen excess.

During the study, the Investigator will determine if increased doses of replacement FVIII or use of bypassing agents is appropriate.

It is recommended that Investigators discontinue the use of bypassing agents once the inhibitor titer is <0.6 BU/mL (negative titer, or values considered negative per local laboratory reference) or once rFVIIIFc provides sufficient hemostatic control, as judged by the Investigator.

The prophylactic use of bypassing agents in subjects with confirmed or suspected inhibitors is permitted; however, the Investigator must inform the Sponsor Medical Monitor and document the rationale for such use.

Throughout the ITI Period, rFVIIIFc administration, bypassing agent administration, and any bleeding episodes will be collected by the subject and/or his caregiver in a study-specific EPD.

EPD data will be reviewed by the Investigator in an ongoing basis and discussed with the subject at each visit.

CONFIDENTIAL

### 7.2.2.2. ITI Outcome

ITI outcome will be assessed on an ongoing basis. Subjects may achieve 1 of 4 outcomes: treatment failure, early withdrawal (outcome not determinable) during the ITI Period, partial success, or ITI success.

#### Early withdrawal (Outcome not determinable)

- Unable to determine outcome due to withdrawal during the ITI Period

#### Treatment failure

Treatment failure is defined as fulfilling one of the following criteria:

- No downward trend of at least 20% in the inhibitor titer in a 6-month (24-week) period after the initial 3 months (12 weeks) during the ITI Period (assessed at the Week 36 [Month 9] Visit).
- Presence of a sustained positive inhibitor ( $\geq 0.6$  BU/mL) after 48 weeks (12 months) of ITI treatment.
- Negative inhibitor titer without achieving either of the 2 PK parameters of ITI success after 48 weeks (12 months) of ITI treatment:
  - $IR \geq 1.32$  IU/dL per IU/kg OR
  - $t_{1/2} \geq 7$  hours

Subjects who have been determined to have failed ITI will then proceed to the End of Treatment (EOT) Visit.

#### Partial success

Partial success is defined as achieving negative inhibitor titer and one of the PK parameters of ITI success:  $IR \geq 1.32$  IU/dL per IU/kg OR  $t_{1/2} \geq 7$  hours.

The determination of partial success will be made only among subjects who have completed the maximum period of 48 weeks (12 months) of ITI treatment but do not fulfill the criteria for ITI success or treatment failure

Subjects who have been determined to have achieved only partial success will then proceed to EOT Visit.

#### ITI success

ITI success is defined as achieving all 3 of the following criteria based on local laboratory results:

- Confirmed negative inhibitor titer ( $< 0.6$  BU/mL by the Nijmegen-modified Bethesda assay) based on 2 consecutive negative inhibitor assessments within 2 weeks ( $\pm 3$  days); determination of negative titer based on the Bethesda assay is acceptable at sites that have not yet adopted the Nijmegen-modified Bethesda assay

CONFIDENTIAL

The information contained herein may not be used, disclosed, or published without the written consent of  
Bioverativ Therapeutics Inc.

Page 41

VV-CLIN-0542000 3.0

- IR  $\geq$ 1.32 IU/dL per IU/kg, representing  $\geq$ 66% of the expected IR 2 IU/dL per IU/kg ([SmPC](#); [USPI](#)), at 2 consecutive assessments performed within 2 to 4 weeks
- $t_{1/2} \geq$ 7 hours

[figure not shown]
CONFIDENTIAL

The information contained herein may not be used, disclosed, or published without the written consent of  
Bioverativ Therapeutics Inc.

Page 42

VV-CLIN-0542000 3.0

**Figure 2 Flow Diagram for Assessment of ITI Outcome**

Abbreviations: BU=Bethesda unit; IR=incremental recovery; ITI=immune tolerance induction;  $t_{\frac{1}{2}}$ =half-life.

After confirmed negative inhibitor titer (<0.6 BU/mL), it is stated 'Perform these assessments (i.e. inhibitor titer every 2 weeks, and IR every 2 weeks) for the remainder of the ITI Period after negative titer (< 0.6 BU/mL) is confirmed'. Although this means that the sample for IR is drawn at the visit for the confirmatory negative inhibitor titer, however, the interpretation of the IR result will be performed after the negative inhibitor titer is confirmed.

CONFIDENTIAL

The information contained herein may not be used, disclosed, or published without the written consent of  
Bioverativ Therapeutics Inc.

Page 43

### **7.2.3. Downtitration (Dose Adjustment) Between ITI Treatment and the Tapering Period**

If FVIII activity levels rise above 200 IU/dL, after the inhibitors are negative but before all of the ITI success criteria are met, the dose will be adjusted according to Investigator judgment to maintain the FVIII activity levels between 100 and 200 IU/dL. This dose adjustment will not be considered part of the Tapering Period, and the subject will maintain the schedule of assessments per the ITI Period.

Once  $t_{1/2}$  has been determined to be  $\geq 7$  hours, the Investigator may have a Tapering Initiation Visit and/or a Tapering Initiation Telephone Call. If the subject has already begun downtitration from the 200 IU/kg/day ITI dose, the subject will return for the next scheduled visit (the Tapering Initiation Visit) 2 weeks from the visit at which  $t_{1/2}$  was determined to be  $\geq 7$  hours. If the subject has not already downtitrated when  $t_{1/2}$  is determined to be  $\geq 7$  hours, the Investigator can make a telephone call to instruct the subject to begin downtitrating immediately (Tapering Initiation Telephone Call). Subject's subsequent visit, which will occur 2 weeks from the visit at which  $t_{1/2}$  was determined to be  $\geq 7$  hours, will be the Tapering Initiation Visit.

### **7.2.4. Tapering Period**

Subjects who have met the criteria for ITI success will enter the Tapering Period. Further details about the recommended dosing regimen for tapering are described in Section 11. Subjects with bleeding episodes during the Tapering Period will be tested for recurrence of inhibitors and monitored for relapse.

During the Tapering Period, treatment with bypassing agents may be considered if bleeding is unresponsive to treatment with rFVIIIFc (see Section 7.2.2.1). Testing for recurrence of inhibitors will be performed throughout the Tapering and Follow-Up Periods.

Subjects will visit the clinic 2 and 4 weeks after the first visit in the Tapering Period and then every fourth week for a minimum of 16 weeks (4 months). The duration of the Tapering Period may be modified by the Investigator with the Sponsor Medical Monitor's approval based on the subject's clinical response. If the Tapering Period exceeds 16 weeks (4 months), unscheduled visits will be performed every 4 weeks (1 month) or per the Investigator's judgment.

During the Tapering Period, subjects will undergo procedures and assessments at designated visits per the schedule of events (see Table 2). At each visit, samples for inhibitor titer and IR assessments will be drawn and sent to the local and central laboratories to monitor for relapse.

If the subject experiences bleeding during the Tapering Period, the treatment of the bleeding will be left to the discretion of the Investigator. During the Tapering Period, treatment with bypassing agents may be considered if bleeding is unresponsive to treatment with rFVIIIFc (see Section 7.2.2.1).

Throughout the Tapering Period, rFVIIIFc administration, bypassing agent administration, and any bleeding episodes will be collected by the subject and/or his caregiver in the EPD. The EPD data will be reviewed by the Investigator on an ongoing basis and discussed with the subject at each visit.

CONFIDENTIAL

The information contained herein may not be used, disclosed, or published without the written consent of Bioverativ Therapeutics Inc.

Page 44

### Relapse

If a subject experiences bleeding episodes that cannot be controlled with the use of rFVIIIFc, further investigation for relapse may be warranted.

Relapse is defined as the occurrence of the following (with or without clinical signs or symptoms) after complete ITI success, based on the International ITI criteria ([Hay & DiMichele, 2012](#)):

- A positive inhibitor ( $\geq 0.6$  BU/mL using the Nijmegen assay) on 2 consecutive assessments performed within 2 to 4 weeks; determination of positive titer based on the Bethesda assay is acceptable at sites that have not yet adopted the Nijmegen-modified Bethesda assay.

AND

- An IR  $<1.32$  IU/dL per IU/kg (representing  $<66\%$  of the expected IR) on 2 consecutive assessments performed within 2 to 4 weeks.

If any assessments indicate the possibility of relapse at any time during the Tapering or Follow-Up Period, the tests must be repeated at the following visit to confirm relapse. A subject with confirmed relapse (i.e., confirmation of both of the above criteria in 2 consecutive assessments) must complete the EOT Visit. At EOT,  $t_{1/2}$  will be assessed and recorded.

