## Endpoints

The primary endpoint of this study is time to tolerization with a maximum of 12 months (48 weeks) of ITI treatment offered in the study (tolerization defined as inhibitor titer  $<0.6$  BU/mL, rFVIIIFc incremental recovery [IR] of  $\geq 66\%$  of expected, and half-life [ $t_{1/2}$ ] of  $\geq 7$  hours).

The secondary endpoints are as follows:

- ITI success
  - Confirmed negative titers consisting of 2 consecutive negative inhibitor assessments within 2 weeks ( $\pm 3$  days) based on local laboratory results  $<0.6$  BU/mL by the Nijmegen-modified Bethesda assay; determination of negative titer based on the Bethesda assay is acceptable at sites that have not yet adopted the Nijmegen-modified Bethesda assay.
  - IR  $\geq 1.32$  IU/dL per IU/kg in 2 consecutive assessments representing  $\geq 66\%$  of the expected IR 2 IU/dL per IU/kg. ([SmPC](#); [USPI](#))
  - $t_{1/2} \geq 7$  hours.
- Occurrence of relapse (defined as confirmed positive inhibitor titer  $\geq 0.6$  BU/mL), abnormal recovery after tolerance is achieved, and  $t_{1/2} < 7$  hours) during the Tapering or Follow-Up Periods
- Number of bleeding episodes during the ITI Period and during the 48-week (12-month) period after successful ITI performed with rFVIIIFc
- Adverse events and serious adverse events
- Number of days away from work or school
- Number of hospitalization days
- Adherence (defined as percentage of administered doses

CONFIDENTIAL

The information contained herein may not be used, disclosed, or published without the written consent of Bioverativ Therapeutics Inc.

versus planned doses)

- Consumption of rFVIIIFc (measured in total rFVIIIFc use)

The exploratory endpoints are as follows:

[REDACTED]  
[REDACTED]  
[REDACTED]  
[REDACTED]  
[REDACTED]  
[REDACTED]  
[REDACTED]  
[REDACTED]

The exploratory endpoint [REDACTED]  
[REDACTED] will be reported outside the clinical  
study report.

Study Design:

An open-label, single-arm, interventional, multicenter study designed to explore the use of rFVIIIFc for ITI in subjects with severe hemophilia A, who are undergoing ITI treatment for the first time.

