The information contained herein may not be used, disclosed, or published without the written consent of Bioverativ Therapeutics Inc.

Page 27

Activities	Tapering Period 	Follow-Up Period 	EOT 	
	Tapering Initiation Visit/Telephone Call,  Week 2, 4, 8, 12, and 16 Visits	Week 28 and 40 Visits 	EOT Visit	Final Safety Follow-Up
	Starting at ITI success and continuing for a minimum of 16 weeks with visits after 2 weeks ( $\pm 3$ days), 4 weeks ( $\pm 1$ week), and then every 4 th week ( $\pm 1$ week)	Week 28 and 40 visits ( $\pm 2$ weeks)  following ITI success	Week 48 visit ( $\pm 2$ weeks) following ITI success OR upon relapse	7 to 14 days after EOT Visit
Concomitant Therapy/ Procedures Recording	X	X	X	X

Abbreviations: EOT=End of Treatment; EPD=electronic patient diary; ET=early termination; FVIII=coagulation factor VIII; IR=incremental recovery; ITI=immune tolerance induction; PK=pharmacokinetic; rFVIIIFc=recombinant coagulation factor VIII Fc fusion protein;  $t_{1/2}$ =half-life.

NOTE: inhibitor titer, FVIII activity level,  $t_{1/2}$ , and IR are all assessed at the local laboratory, with confirmation by the central laboratory. The Investigators will use local laboratory results for decision-making purposes.

Hematology, blood chemistry, and urinalysis are assessed only at the local laboratory.

- 1 During the Tapering and Follow-Up Periods, the subject's dose will be adjusted to achieve each subject's prophylactic dose as determined by the Investigator. Minimum Tapering Period is 16 weeks (4 months). Subjects who relapse during the Tapering Period (i.e., who have confirmation of inhibitor development AND who have confirmed decrease of IR, with or without clinical signs or symptoms) will proceed immediately to the EOT Visit. Subjects will be closely monitored during the Tapering Period for potential relapse.  
For Canada specific requirements: see Appendix B.
- 2 Timing of the EOT Visit will vary for subjects, as described in Section 7.2.6.

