- 3 Once  $t_{1/2}$  has been determined to be  $\geq 7$  hours, the Investigator may elect to have a Tapering Initiation Visit and/or a Tapering Initiation Telephone Call. If the subject has already begun downtitration from the 200 IU/kg/day ITI dose prior to ITI success, the subject will return for the next scheduled visit (the Tapering Initiation Visit) 2 weeks from the visit at which  $t_{1/2}$  was determined to be  $\geq 7$  hours. If the subject has not already downtitrated when  $t_{1/2}$  is determined to be  $\geq 7$  hours, the Investigator can make a telephone call to instruct the subject to begin downtitrating immediately (Tapering Initiation Telephone Call) Subject's subsequent visit, which will occur 2 weeks from the visit at which  $t_{1/2}$  was determined to be  $\geq 7$  hours, will be the Tapering Initiation Visit (see Section 7.2.3).
- 4 Subjects who do not achieve ITI success within 48 weeks (12 months) will proceed to the ET/EOT Visit. Subjects who develop inhibitors during the Tapering or the Follow-Up Period (i.e., who relapse) will proceed immediately to the ET/EOT Visit.
- 5 Vital signs include blood pressure, pulse rate, respiratory rate, and body temperature. Postdose assessments following in-clinic injections will be taken prior to and 20 ( $\pm 5$ ) minutes after the end of the rFVIIIFc injection (if dosing occurs at the visit).
- 6 Hematology, blood chemistry, and urine dipstick are to be collected every 12 weeks (3 months) during the Tapering Period. These assessments will also be collected at the EOT Visit.
- 7 Dipstick urinalysis, including a protein reading; if the protein reading is positive ( $\geq 1+$ ), a full laboratory urinalysis will be required.

CONFIDENTIAL

The information contained herein may not be used, disclosed, or published without the written consent of  
Bioverativ Therapeutics Inc.

- 8 Subjects will be advised to delay administration of their daily dose of rFVIIIFc until after the sample for inhibitor testing is taken. An unscheduled visit may be required to repeat inhibitor testing under this protocol to obtain a sample to confirm a positive inhibitor test result.

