- 9 If ITI success is declared, a sample will be collected at the first visit in the Tapering Period. If partial success or failure is declared, a sample will be collected at the EOT Visit. The samples will be collected as allowable based on subject weight and institutional practice regarding blood draw restrictions for pediatric subjects.
- 10 Takes place at each visit in which IR or  $t_{1/2}$  is being assessed.
- 11 Subjects will be advised to delay administration of the remainder of their daily dose of rFVIIIFc until after the sample for IR is taken. Blood samples will be collected for analysis of rFVIIIFc activity for assessment of IR starting at the visit for confirmed negative titers and at all consecutive visits, except for those visits where samples for rFVIIIFc  $t_{1/2}$  determination are drawn, as IR will be determined from the same samples. Blood samples will be taken at predose (within 30 minutes prior to the start of injection) and postdose ( $30 \pm 5$  minutes after the start of injection). If any assessments indicate the possibility of relapse at any time during the Tapering or Follow-Up Period, the test must be repeated at the following visit to confirm relapse (i.e., IR <66%).
- 12 Subjects will be advised to delay administration of the remainder of their daily dose of rFVIIIFc until after the final post-dose sample for  $t_{1/2}$  is taken (i.e., up to 48 hours post dose). PK assessments for  $t_{1/2}$  determination are to be performed when the subject is in a nonbleeding state and after at least a 24-hour washout (see [Table 3](#)).
- 13 A sample for FVIII activity can be collected as needed per Investigator discretion. FVIII activity levels can be derived from IR samples; therefore, a separate blood draw for FVIII activity assessment is not required.
- 14 It is recommended that subjects/caregivers enter dosing information immediately after an injection or within a maximum of 7 days.

CONFIDENTIAL

The information contained herein may not be used, disclosed, or published without the written consent of  
Bioverativ Therapeutics Inc.

Page 29

VV-CLIN-0542000 3.0

Details on sampling for rFVIIIFc are described in Section 13.1.3 and **Table 3**.

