Subjects must not be currently bleeding and are required to have at least a 24-hour washout prior to the rFVIIIFc  $t_{1/2}$  predose sample collection. A dose of 50 IU/kg of rFVIIIFc for assessments will be delivered via a slow push IV injection over several minutes, at a rate of administration determined by the subject's comfort level. Volume and units of factor infused must be calculated and recorded using the actual potency as described in the DHA included in the Study Reference Manual. Subjects will not have any additional doses of rFVIIIFc during the PK Sampling Period. If emergency dosing is required during the  $t_{1/2}$  Sampling Period, inform the Sponsor and the  $t_{1/2}$  assessment will be rescheduled.

Once the final sample for  $t_{1/2}$  has been collected, the subjects can be given their daily ITI dose.

Subjects have fulfilled the third and last criterion for ITI success after a FVIII activity  $t_{1/2} \geq 7$  hours has been determined by the local and/or central laboratories (see Section 7.2.2.2).

During the Tapering and Follow-Up Period, if a subject meets the criteria for relapse, he will then proceed to the EOT Visit, at which  $t_{1/2}$  will be assessed.

CONFIDENTIAL

The information contained herein may not be used, disclosed, or published without the written consent of Bioverativ Therapeutics Inc.

Page 59

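### Relapse is worded in two ways, no repeat is required inside its own 2-to-4-week window from Week 16 on, and its 48-week rate is a crude proportion

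*Protocol*

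**What the plan says.** **Objective.** Protocol 6.2 sets out to describe the relapse rate over the 48 weeks after successful ITI.

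**Operative definition.** Protocol 7.2.4 requires titer at or above 0.6 BU/mL and IR below 1.32 IU/dL per IU/kg, each "on 2 consecutive assessments performed within 2 to 4 weeks". Table 2 footnote 1 uses the same two elements, for subjects "who have confirmation of inhibitor development AND who have confirmed decrease of IR". SAP 4.4.1.1 also uses titer and IR, and states no window.

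**Endpoint wording.** The synopsis, Protocol 6.2 and SAP Table 1 list a confirmed positive titer, then "abnormal recovery after tolerance is achieved, and" half-life below 7 hours. SAP Table 1 puts all three inside one bracket. In the protocol the bracket closes after the titer. Half-life is measured later: under Protocol 13.1.3.1, "if a subject meets the criteria for relapse, he will then proceed to the EOT Visit", where it is assessed.

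**Inhibitor-only wording.** Table 2 footnote 4 says: "Subjects who develop inhibitors during the Tapering or the Follow-Up Period (i.e., who relapse) will proceed immediately to the ET/EOT Visit". Protocol 15.3.2 labels a confirmed positive inhibitor after ITI success as relapse of an inhibitor for SAE reporting.

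**Repeat testing.** If relapse is possible, 7.2.4 says "the tests must be repeated at the following visit to confirm relapse", and footnote 11 says "the test must be repeated at the following visit to confirm relapse". Footnote 8 adds: "An unscheduled visit may be required to repeat inhibitor testing". Section 7.3 permits unscheduled inhibitor and IR evaluations. If tapering runs past 16 weeks, 7.2.4 adds visits every 4 weeks or as the investigator judges.

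**Analysis.** Protocol 16.2.2.2 and SAP 4.4.1.2 give the proportion of patients with ITI success who relapse, on the Tapering Period full analysis set (TPFAS), and describe time to relapse among relapsers only. SAP 4.1 has a general Kaplan-Meier rule for event times, on the ITI full analysis set (ITIFAS).

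**The concern.** The same patient can be classed differently depending on which sentence is applied. With a confirmed inhibitor, low IR and half-life of 7 hours or more, he has relapsed under 7.2.4 and SAP 4.4.1.1, but not under SAP Table 1. With a confirmed inhibitor and normal IR, he has not relapsed under 7.2.4, but footnote 4 and 15.3.2 use the word for him.

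From Week 16 on, a site that repeats the tests at the next scheduled visit follows the repeat rule to the letter and still misses the window in the definition. A real late relapse may then never be confirmed as 7.2.4 requires.

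The crude proportion also does not match an objective stated over 48 weeks, because a patient who leaves at, say, Week 20 without relapse is counted as relapse-free to Week 48.

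**Working it through.** The plan gives no numerical target or assumed rate for relapse, so there is no figure of its own to reproduce.

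**1. Gaps between scheduled visits.** Inputs are from Protocol Table 2, in weeks after ITI success: Week 2 (±3 days); Weeks 4, 8, 12, 16 (±1 week); Weeks 28, 40, 48 (±2 weeks). Nominal gap = later week − earlier week. Range = nominal gap ± the sum of the two visit windows.

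| First signal → next visit | Nominal | Range |
|---|---|---|
| 2 → 4 | 2 | 0.6 to 3.4 |
| 4 → 8, 8 → 12, 12 → 16 | 4 each | 2 to 6 |
| 16 → 28 | 12 | 9 to 15 |
| 28 → 40 | 12 | 8 to 16 |
| 40 → 48 | 8 | 4 to 12 |
| 48 → none | no titer or IR sampling | – |

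Up to Week 12 the schedule nominally meets the window. A first signal at Week 16 or 28 can never be repeated within 4 weeks at the next scheduled visit. One at Week 40 can be only at the extremes (Week 42, then Week 46). After Week 48, Table 2 has only a safety contact 7 to 14 days later, with no titer or IR sample. If tapering weeks are counted from a Tapering Initiation Visit 2 weeks after the half-life visit, the 16 → 28 gap becomes 10 (7 to 13), still beyond 4.

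**2. Dating.** SAP 4.4.1.1 does not say whether the first or the confirming abnormal result dates a relapse. Inside the window the choice moves time to relapse by 2 to 4 weeks, that is 14 to 28 days.

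**3. Crude proportion against the 48-week risk.** The documents give no relapse or dropout rates, so constant hazards are assumed, with 48-week relapse p and dropout d each from 10% to 30%.

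λr = −ln(1−p), λd = −ln(1−d), expected crude proportion = λr/(λr+λd) × [1 − exp(−(λr+λd))].

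For p = d = 20%: the two hazards are equal and exp(−(λr+λd)) = 0.8 × 0.8 = 0.64, so the crude proportion is 0.5 × 0.36 = 18.0%.

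| True p | d = 10% | d = 20% | d = 30% |
|---|---|---|---|
| 10% | 9.50% | 8.98% | 8.44% |
| 20% | 19.02% | 18.00% | 16.93% |
| 30% | 28.56% | 27.07% | 25.50% |

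The understatement is 0.50 to 4.50 points, or 4.8% to 15.6% relative.

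A harsher illustration assumes 10 patients, 2 relapses, and k patients leaving before either relapse. Crude = 2/10 = 20.0%. Kaplan-Meier = 2/(10−k) = 22.2%, 25.0% or 28.6% for k = 1, 2 or 3.

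**4. Scale.** The exact (Clopper-Pearson) 95% interval for 2/10 is 2.5% to 55.6%. Reclassifying one patient moves the proportion by 1/17 = 5.9 points if all 17 planned subjects entered tapering, or 1/10 = 10 points with 10.

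**The case against.** **The definition is consistent wherever it is applied.** Protocol 7.2.4, footnote 1 and SAP 4.4.1.1 agree, and half-life is recorded at end of treatment, so a disputed case can be classified either way afterwards. This largely stands. A reader might infer that relapses will be lost through the half-life criterion. The documents do not support that, because SAP 4.4.1.1 governs the derivation. What remains is a contradiction inside the SAP, between Table 1 and 4.4.1.1, and a less clear one in the protocol because of its bracket.

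**The following visit need not be a scheduled one.** Section 7.2.4 does not say scheduled, its definition carries the window, and unscheduled titer and IR repeats are allowed. Bleeding during Tapering or Follow-Up also triggers inhibitor testing off schedule. So it would be wrong to conclude that late relapses cannot be confirmed. It would also be wrong to treat the time after Week 12 (36 of 48 weeks, 75%) as a share of relapses, since it is a share of calendar time only. What remains is that no text requires a timed titer and IR repeat in Follow-Up or after a first signal at Week 48.

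**SAP silence is not a rival rule.** The SAP is based on the July 2019 protocol, so confirmed can carry the 7.2.4 window. Elsewhere the first result of a confirmed pair sets the date (Protocol Table 1 footnote 1, SAP 4.3.4). This stands: window and dating are missing detail, settled in a sentence.

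**The crude TPFAS proportion is prespecified, and SAP 4.1 already offers Kaplan-Meier.** The first part is true, so the protocol needs the change too. But ITIFAS includes patients who never reached ITI success and so have no time origin for relapse, and 4.4.1.2 does not carry the rule over. Using TPFAS for the follow-up-only proportion might also look like an error, since SAP Table 2 assigns that period to the follow-up set. It is a defensible choice, because a common denominator lets the two period proportions add up to the combined one.

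**Conclusion.** The point holds in three parts: the half-life wording in SAP Table 1 contradicts the operative definition; the mandated repeat does not secure the 2-to-4-week confirmation from Week 16 on; and the crude proportion does not estimate a 48-week rate when patients leave early.

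The effect is modest. The gaps follow directly from Table 2. The bias figure rests on assumed constant hazards and assumed dropout; it vanishes if nobody leaves early, and exceeds the tabled range if leavers go before any relapse, as in the 10-patient illustration. Either way it is well inside the sampling error at this size. A claim that the reported relapse rate will be materially wrong would go beyond the documents: relapse is a secondary, descriptive endpoint with no hypothesis test, and SAP 4.3.4 lists each patient's period durations, relapse status and time to relapse. The case for acting is that single patients weigh heavily here and the remedies are cheap.

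**What to change.** **Protocol**
- Delete half-life below 7 hours from the relapse wording in the synopsis and 6.2.
- Align Table 2 footnotes 4 and 11, and the relapse label in 15.3.2, with 7.2.4. A confirmed inhibitor alone can remain a reportable SAE under another name.
- In 7.2.4, require both titer and IR to be repeated 2 to 4 weeks after any possible relapse signal, by unscheduled visit where needed, including after a first signal at Week 48.
- Update 16.2.2.2 to match the analysis below.

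**SAP**
- Delete the half-life element from relapse in Table 1.
- Date relapse at the first abnormal result of the confirmed pair, and list signals not confirmed in the window.
- Beside the crude proportion, add a Kaplan-Meier 48-week relapse estimate on TPFAS, from ITI success, censored at the last titer/IR assessment. State that the ITIFAS rule in 4.1 does not apply to relapse.
- Keep TPFAS for the period proportions.

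**Cost.** Wording changes in both documents, occasional unscheduled visits that 7.3 already permits, one listing and one table. The Kaplan-Meier estimate will be imprecise at this size and assumes that leaving is unrelated to relapse risk.
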